2.1.12. Health Outcomes Listings

| Health Outcomes Listings | | | | |
|--------------------------|-------------------|------------|---|--|
| New output number | Old output number | Population | Title | Major modifications since original RAP |
| Health Outcomes Listings | | | | |
| 24.01. | 24.04 | ITT | Health Care Resource Utilization (Year 1&2) | |

2.1.13. Biomarkers Tables

| Biomarkers Tables | | | | |
|-------------------|-------------------|------------|---|--|
| New output number | Old output number | Population | Title | Major modifications since original RAP |
| Immunoglobulins | | | | |
| 25.01. | 25.02 | ITT | Immunoglobulin Levels Change from Baseline by Visit among Subjects who Completed Week 52 On Treatment (Observed) (Year 1&2) | |

| Biomarkers Tables | | | | |
|---|--------------------------|-------------------|---|---|
| New output number | Old output number | Population | Title | Major modifications since original RAP |
| 25.02. | 25.03 | ITT | Immunoglobulin Levels Shifts from Baseline by Visit among Subjects who Completed Week 52 On Treatment (Observed) (Year 1&2) | |
| Autoantibodies | | | | |
| 25.03. | 25.06 | ITT | Autoantibody Levels Change from Baseline by Visit among Subjects who Completed Week 52 On Treatment (Observed) (Year 1&2) | |
| 25.04. | 25.07 | ITT | Autoantibody Levels Change from Baseline by Visit among Subjects Positive at Baseline who Completed Week 52 On Treatment (Observed) (Year 1&2) | |
| 25.05. | 25.08 | ITT | Autoantibody Levels Shifts from Baseline by Visit among Subjects who Completed Week 52 On Treatment (Observed) (Year 1&2) | |
| Complement | | | | |
| 25.06. | 25.11 | ITT | Complement Levels Change from Baseline by Visit among Subjects who Completed Week 52 On Treatment (Observed) (Year 1&2) | |
| 25.07. | 25.12 | ITT | Complement Levels Change from Baseline by Visit among Subjects with Low Complement at Baseline who Completed Week 52 On Treatment (Observed) (Year 1&2) | |
| 25.08. | 25.13 | ITT | Complement Levels Shifts from Baseline by Visit among Subjects who Completed Week 52 On Treatment (Observed) (Year 1&2) | |
| B Cells, T Cells and B-Lymphocyte Stimulator | | | | |
| 25.09. | 25.15 | ITT | B Cells, T Cells and B-Lymphocyte Stimulator Change from Baseline by Visit among Subjects who Completed Week 52 On Treatment (Observed) (Year 1&2) | |

2.1.14. Biomarkers Figures

| Biomarkers Figures | | | | |
|--------------------------|-------------------|------------|--|---|
| New output number | Old output number | Population | Title | Major modifications since original RAP |
| Biomarker Figures | | | | |
| 25.01. | NEW | ITT | Immunoglobulin Levels Change from Baseline by Visit among Subjects who Completed Week 52 On Treatment (Observed) (Year 1&2) | 
 • New output (omission in original RAP) |
| 25.02. | NEW | ITT | Autoantibody Levels Change from Baseline by Visit among Subjects who Completed Week 52 On Treatment (Observed) (Year 1&2) | 
 • New output (omission in original RAP) |
| 25.03. | NEW | ITT | Complement Levels Change from Baseline by Visit among Subjects who Completed Week 52 On Treatment (Observed) (Year 1&2) | 
 • New output (omission in original RAP) |
| 25.04. | NEW | ITT | B Cells, T Cells and B-Lymphocyte Stimulator Change from Baseline by Visit among Subjects who Completed Week 52 On Treatment (Observed) (Year 1&2) | 
 • New output (omission in original RAP) |

2.1.15. Biomarkers Listings

| Biomarkers Listings | | | | |
|---------------------------|-------------------|------------|---|--|
| New output number | Old output number | Population | Title | Major modifications since original RAP |
| Biomarker Listings | | | | |
| 25.01. | 25.01 | ITT | Biomarker Results (Year 1&2) | |
| 25.02. | 25.02 | ITT | B Cells, T Cells and B-Lymphocyte Stimulator Results (Year 1&2) | |

2.1.16. Pharmacokinetic Tables

| PK Tables | | | | |
|-------------------|-------------------|------------|--|--|
| New output number | Old output number | Population | Title | Major modifications since original RAP |
| 26.01. | 26.01 | PK | Belimumab Concentrations (ug/mL) among Subjects who Completed Week 52 On Treatment (Observed) (Year 1&2) | |

2.1.17. Pharmacokinetic Figures

There are no PK Figures to produce.

2.1.18. Pharmacokinetic Listings

| PK Listings | | | | |
|-------------------|-------------------|------------|---|--|
| New output number | Old output number | Population | Title | Major modifications since original RAP |
| 26.01. | 26.01 | PK | Serum Belimumab PK Concentrations (Observed) (Year 1&2) | |

2.2. New ‘Intent-to-Treat Year 2’ Population

An additional population has been defined for use in any Study Population and Adverse Event table that presents data only for Year 2.

The ‘Intent-to-Treat Year 2’ population is defined as “All ITT population participants who are ongoing in Year 2. This includes subjects who confirm that they are continuing in the study for Year 2 and/or have an exposure date or early withdrawal visit after the Week 52 visit date.”

2.3. Biomarker and Pharmacokinetic (PK)

2.3.1. Specifications in the original RAP

The original RAP gave minimal information about the data that should be used in the Biomarker and PK analyses for the Year 2 reporting.

For Biomarkers, the original RAP Section 10.1 stated that “The Year 1&2 analyses will be performed on the observed data for subjects who completed Week 52 on treatment (Ongoing and on treatment at Week 52 analysis as defined in Section 7.1.5). No imputation will be performed for missing data (data post re-start Belimumab will not be considered).”

For PK, the original RAP Section 11 gave no details.

Section 2.3.2 clarifies the approach that will be used for Year 2 reporting of both Biomarker and PK data. The intended approach for Biomarkers (described above) is utilised, explained further and broadened so that the method is also consistent for PK analyses.

2.3.2. Clarifications for the Year 2 reporting

The original definition of subjects who completed Week 52 on treatment (referenced in the original RAP Section 7.1.5) was based on the MITT population as it was intended to be used for Efficacy data. However, for Biomarker and PK analyses, this needs to be modified to be based on all subjects from the ITT population. Therefore, it has been copied directly but with the ITT population as the original population as follows:

All ITT population Arm A and Arm B participants who are ongoing after 52 weeks of the planned double-blind treatment period who received all of both IV doses of rituximab or rituximab-placebo, and did not have more than 28 consecutive days from baseline to Week 51 without a belimumab dose; includes ITT population Arm C subjects who remained on open-label belimumab through Week 52 and did not have more than 28 consecutive days baseline to Week 51 without a belimumab dose.

For Arms A&B, the Year 1&2 analyses will be performed on the observed data collected in Year 1 and prior to any re-start Belimumab in Year 2, for subjects who completed Week 52 on treatment.

For Arm C, the Year 1&2 analyses will be performed on the observed data up to IP discontinuation, for subjects who completed Week 52 on treatment.

No imputation will be carried out for missing data.

Note that the PK outputs will be presented for the PK population.

Signature Page for 205646 TMF-13873132 v1.0

| | |
|------------------------------|---|
| Reason for signing: Approved | Name: PPD Role: Approver Date of signature: 22-Jul-2021 12:38:41 GMT+0000 |
|------------------------------|---|

| | |
|------------------------------|---|
| Reason for signing: Approved | Name: PPD Role: Approver Date of signature: 22-Jul-2021 14:16:22 GMT+0000 |
|------------------------------|---|

Signature Page for TMF-13873132 v1.0

| | |
|-------------------------|--|
| Division | : Worldwide Development |
| Information Type | : Reporting and Analysis Plan Addendum |
| Title | : Reporting and Analysis Plan Addendum for 205646, a Phase 3, Multi-Center, Randomized, Double-Blind, Placebo-Controlled, 104-Week Study to Evaluate the Efficacy and Safety of Belimumab Administered in Combination with Rituximab to Adult Subjects with Systemic Lupus Erythematosus (SLE) |
| Compound Number | : GSK1550188 |
| Effective Date | : 08-OCT-2020 |

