During Weeks 53 to 104, additional treatment may be given if the investigator believes the participant would benefit because he/she: a) responded to study treatment but did not meet the primary efficacy endpoint, or b) responded to study treatment but subsequently experienced increasing disease activity which requires additional therapy. Additional treatment may include open-label belimumab, corticosteroids (>5 mg/day), and/or immunosuppressants, and will be administered at the discretion of the investigator. Treatment with open-label rituximab is allowed within the protocol, but is not encouraged. Belimumab will be provided by the sponsor for those participants who reinitiate treatment with belimumab, but additional treatment with rituximab and/or other medications will not be provided by the sponsor. NOTE: These participants will be considered treatment failures for the Week 64 efficacy analyses if the additional treatment (see above) occurs before the Week 64 visit, and for the Week 104 efficacy analyses if the additional treatment occurs before the Week 104 visit. Participants who are deemed treatment failures will continue to be followed in the study and have all efficacy and safety assessments performed.

In the event that a participant discontinues the study or withdraws consent early, an Early Withdrawal visit 1-4 weeks after last dose of study treatment and a Follow Up visit 8 weeks after the last dose of study treatment should be scheduled. Additionally, an attempt

205646

will be made to ascertain survival status at approximately 52 and 104 weeks after the first dose of study treatment.

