Participants in Arm C will continue to receive belimumab during Weeks 53 to 104. Participants in Arm C who, in the opinion of the investigator, require additional treatment, may receive rescue therapy including corticosteroids >5 mg/day of a prednisone equivalent and/or new, additional or increased immunosuppressants at the investigator's discretion. Treatment with open-label rituximab is allowed, but not encouraged. Other SLE treatments, including rituximab, will not be provided by the study. In these situations, the participants in Arm C would be considered treatment failures for the efficacy endpoints. Participants who are declared treatment failures will be encouraged to remain in the study and continue to receive all safety and efficacy assessments.

Management of additional SLE therapy, including required laboratory tests and other procedures, is described in the SRM.

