2.8. LLDAS – clarification of endpoint definition (RAP Section 15.6.9)

Clarifications have been made to the LLDAS endpoint definition table in RAP Section 15.6.9. for the criteria of “well tolerated standard maintenance doses of immunosuppressive drugs and approved biological agents, excluding investigational drugs”.

Firstly, the RAP Section 15.6.9 and protocol Section 7.7.14 refer to “Cyclosporine”, however the MedDRA dictionary name is “Ciclosporin”.

Secondly the existing text in RAP Section 15.6.9 (shown below) has been clarified to include the additional text shown in bold. This additional text makes it clearer that the Anti-TNF therapy and other biologics listed are just examples and it also provides additional examples of other biologics based on the Year 1 blinded data:

“Not to be taken within 28 days prior to the assessment:

- Intravenous Cyclophosphamide
- Other investigation agent

- Anti-TNF therapy (e.g. adalimumab, etanercept, infliximab)
- Other biologics (e.g. abatacept, anakinra, **commercial rituximab, tocilizumab**)
- IVIG
- Plasmapheresis”

The following sentence has also been added to clarify the use of commercial Belimumab:
“Subjects can take commercial Belimumab IV or SC and this doesn’t prevent them from being a responder on this criteria for the LLDAS.”.

| | |
|-------------------------|-------------------------------------|
| Division | : Worldwide Development |
| Information Type | : Reporting and Analysis Plan (RAP) |

| | |
|------------------------|---|
| Title | : Reporting and Analysis Plan for 205646, a Phase 3, Multi-Center, Randomized, Double-Blind, Placebo-Controlled, 104-Week Study to Evaluate the Efficacy and Safety of Belimumab Administered in Combination with Rituximab to Adult Subjects with Systemic Lupus Erythematosus (SLE) |
| Compound Number | : GSK1550188 |
| Effective Date | : 5-AUG-2020 |

| | |
|--|--|
| Description: | |
| 
 • The purpose of this RAP is to describe the planned analyses and output to be included in the Clinical Study Report for Protocol 205646. • This RAP is intended to describe the planned efficacy, safety, pharmacokinetics and biomarker analyses required for the study. • This RAP will be provided to the study team members to convey the content of the Statistical Analysis Complete (SAC) deliverable. | |

RAP Author:

| Author | Approval Method |
|---|------------------------|
| PPD Statistics Leader (Rheumatology Biostatistics) | eTMF |

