6.5. Extent of Exposure to Study Treatment

Exposure listings detail the amount of planned study medication that was taken, and re-start medication (belimumab taken in Year 2 for Arms A and B). However they do not include concomitant medication of non-study belimumab or rituximab.

Exposure data for both belimumab and rituximab will be listed for:

- Year 1: Arm A, B, and C for belimumab; and Arms A and B for rituximab/placebo in Year 1 [L11.13].
- Year 2: Arm A&B: Includes late Year 1 doses (taken in year 2) for Belimumab and re-start Belimumab; Arm C belimumab in Year 2 [L21.08].

See Section 15.6.2 for further details.

Belimumab

The extent of exposure to belimumab through Week 52 for Arm A and Arm B and through Week 104 for Arm C will be assessed by examining the duration of exposure to belimumab in days and the total number of injections a subject receives. Duration of exposure in days will be calculated as:

Duration of exposure (days) = (Last injection date – First injection date + 7).

Only complete dates will be used when calculating duration of exposure. First and last injection dates will be used, regardless of any missed doses.

Percent compliance will be calculated as:

$100 * (\text{Number of injections prescribed} - \text{Number of injections missed}) / \text{Number of injections prescribed}$.

The duration of exposure, the total number of injections, and the percent compliance will be summarized using descriptive statistics for the treatment phase. The total number of injections will also be summarized using counts and percentages using the following categories: 1 – 12 doses, 13 – 24 doses, 25 – 36 doses, 37 - 52 and > 52 doses (if applicable). [T11.38]. Similarly, exposure to belimumab in Arm C from Baseline to Week 104 will also be summarized using the following categories: 1 – 12 doses, 13 – 24 doses, 25 – 36 doses, 37 - 52 doses, 53 - 64 doses, 65 - 76 doses, 77 – 88 doses, 89 - 104 doses, and >104 doses (if applicable) [T21.14].

Exposure to belimumab will also be summarized for subjects during Year 2 only. For subjects in Arms A and B this will include incorrectly taken Year 1 medication after

Week 52 and re-start medication [T21.15]. The first dose in Year 2 will be the 1st dose the subject took on the day of or after the Week 52 visit date.

Duration of exposure (days) = (Last injection date – First injection date + 7).

Rituximab

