10.1. Biomarker Change and Percent Change from Baseline Analyses

| |
|---|
| Endpoints |
| The change from baseline and percent change (not for % endpoints) from baseline will be evaluated by visit for each of the biomarkers listed in Table 4 [T15.01-15.02, T15.04-T15.07, T15.09-T15.12, T15.14-T15.15, T25.01-25.02, T25.04-T25.07, T25.09-T25.12, T25.14-T25.15,]. Tables of descriptive statistics for changes in Year 2 relative to at the end of Year 1 will be summarised for immunoglobulins, auto-antibodies and B-Cells [T25.21, T25.22, T25.23]. |
| Population of Interest |
| The Intent-to-Treat population will be used for the analysis. |
| Intercurrent Event Strategy |
| The Year 1 analyses will be performed on the observed data up to IP discontinuation. No imputation will be done for missing data. The Year 1&2 analyses will be performed on the observed data for subjects who completed Week 52 on treatment (Ongoing and on treatment at Week 52 analysis as defined in Section 7.1.5). No imputation will be performed for missing data (data post re-start Belimumab will not be considered). |
| Model Specification |
| Immunoglobulins and Complement An ANCOVA will be used to evaluate the treatment effect controlling for treatment group, baseline SLEDAI-2K score (≤ 9 vs. ≥ 10), baseline immunosuppressant use (use vs. non-use), baseline corticosteroid dose (prednisone equivalent ≤ 10 mg/day vs. > 10 mg/day), and baseline value (continuous). If the distribution of the observed data is not consistent with conducting ANCOVA then a non-parametric rank ANCOVA will also be conducted. Auto-Antibody, B-Cells, T-Cells, and BLYS (Total and Free): A Rank ANCOVA will be used to evaluate the treatment effect controlling for treatment group, baseline SLEDAI-2K score (≤ 9 vs. ≥ 10), baseline immunosuppressant use (use vs. non-use), baseline corticosteroid dose (prednisone equivalent ≤ 10 mg/day vs. > 10 mg/day), and rank baseline value (continuous). |
| Model Checking & Diagnostics |
| For the ANCOVA analysis the Kolmogorov-Smirnov D statistic will be used to test the assumption of normality. Residuals will be reviewed to assess the homogeneity of variance assumption. |

Model Results Presentation

The tables will display:

- Baseline: the number subjects, number of subjects, mean, standard error, standard deviation, median, 25th percentile, 75th percentile, minimum, maximum for each arm

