- the number of subjects, mean, standard error, standard deviation, median, 25th percentile, 75th percentile, minimum, and maximum, for each arm at each visit
- For ANCOVA analysed endpoints the LS Mean, standard error of the LS Mean, treatment difference for each arm, and 95% confidence interval (CI) for the comparison of Arm B vs Arm A; and Arm B vs Arm C will be presented at Weeks 52, 64, and 104
- For all endpoints the p-value for treatment difference for Arm B vs Arm A will be presented at Weeks 52, 64, and 104.

For change from baseline endpoints, a plot of LS means +/- SE or Median +/- Quartiles (dependent on observed data distribution) by visit and treatment group will be provided.

There will also be additional reporting of lab parameters (Haematology, chemistry, urinalysis and other chemistries) to explore the changes in Year 2 relative to at the end of Year 1. Descriptive statistic tables considering the change from Week 52 by visit for Year 2 will be produced [T25.16-25.19].

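### The Year 1&2 biomarker analyses keep data collected after non-study rituximab, although they cut data after re-start belimumab

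*SAP*

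**What the plan says.** Addendum 2, Section 2.3.2, sets the data rule for the end-of-study biomarker and PK outputs. Participants must have completed Week 52 on treatment: in Arms A and B, both infusions in full and no belimumab gap of more than 28 consecutive days; in Arm C, open-label belimumab through Week 52 with the same gap limit. Arms A and B then contribute "observed data collected in Year 1 and prior to any re-start Belimumab in Year 2, for subjects who completed Week 52 on treatment". Arm C contributes observed data until investigational product is discontinued. Nothing is imputed. The Arm A/B rule carries forward RAP Section 10.1, quoted in Addendum 2, Section 2.3.1.

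Protocol Section 7.7.4 says, for Arms A and B and again for Arm C in Year 2: "Treatment with open-label rituximab is allowed, but not encouraged". The Synopsis says the same ("Treatment with open-label rituximab is allowed within the protocol, but is not encouraged") and does not make it conditional on re-starting belimumab.

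The biomarker objective (Protocol Section 4) concerns belimumab with a single cycle of rituximab. For the change-from-baseline analyses RAP Section 10.1 plans: "For all endpoints the p-value for treatment difference for Arm B vs Arm A will be presented at Weeks 52, 64, and 104".

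**The concern.** The restriction to fully dosed participants and the cut at re-start belimumab both aim at the response to the assigned regimen. Keeping values after extra rituximab works against that aim. The rule is not a treatment-policy approach, because data after one form of rescue are dropped. Nor is it limited to the assigned regimen, because data after another form are kept.

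Rituximab is also the rescue most likely to move these measurements. Protocol Section 3.2 describes nearly complete depletion of peripheral CD20+ B cells within hours. At stake is the Year 2 mechanistic evidence: B-cell return, immunoglobulin recovery and BLyS after the study cycle.

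The efficacy analyses do address this. Protocol Section 10.4.1 and RAP Section 15.6.15.2 make non-study rituximab a treatment failure. No matching rule exists for the biomarkers.

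**Working it through.** The plan gives no figure to reproduce. The check is on the wording, followed by an illustration of scale.

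**1. What triggers the cut (Addendum 2, Section 2.3.2, against Protocol Section 7.7.4)**

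| Year 2 event | Cut triggered? | Later values counted in |
|---|---|---|
| Arm A, rituximab, no re-start belimumab | No | Arm A |
| Arm B, further rituximab, no re-start belimumab | No | Arm B |
| Arm C, rituximab while belimumab continues | No | Arm C |
| Arm A or B, rituximab after re-start belimumab | Already cut | Not used |

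The entry condition does not exclude extra rituximab either, so any Year 1 use also stays in. RAP Section 10.1 has the same gap for the Year 1 report: "The Year 1 analyses will be performed on the observed data up to IP discontinuation". Use is not purely hypothetical. Addendum 1, Section 2.8, adds commercial rituximab to its list of other biologics and refers to the Year 1 blinded data, without a count.

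**2. Which results are exposed (Protocol Schedule of Activities, Tables 2 and 4; RAP Sections 10.1 and 10.2)**

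- B-cell subsets are sampled in Year 2 at Weeks 60, 80 and 104. With p-values at Weeks 52, 64 and 104, only Week 104 gives a Year 2 B-cell test.
- Immunoglobulins, anti-dsDNA/ANA and C3/C4 are sampled at every Year 2 visit, as is BLyS in Arms A and B. Weeks 64 and 104 are both exposed.
- Arm C has no Year 2 BLyS sampling and no p-value.
- The shift tables have Fisher tests at Week 52 only. Their Year 2 content is descriptive.

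**3. Direction**

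Let a and b be the mean B-cell counts that Arms A and B would show without extra rituximab, d the mean after it, and f and g the shares of Arms A and B that receive it.

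- Observed Arm A mean = a − f(a − d).
- Observed Arm B mean = b − g(b − d).
- Observed A minus B = (a − b) − f(a − d) + g(b − d).

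The f term shrinks the difference and the g term widens it. The documents give neither share, so the sign of the net change is unknown.

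**4. Scale, on assumed shares**

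(i) With d near zero, k users among 50 qualifying Arm A participants (50 is an assumption; the target is 70) lower the Arm A mean count by k/50: 1/50 = 2%, 3/50 = 6%, 5/50 = 10%.

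(ii) With d = b and g = 0, the difference becomes (1 − f)(a − b). Take target sizes of 70 and 140 (Protocol Section 10.2) and an assumed true difference of 0.5 SD. The standard error is √(1/70 + 1/140) = 0.146 SD, and power = Φ(0.5(1 − f)/0.146 − 1.96).

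| f | Arm A users of 70 | Difference retained | Power |
|---|---|---|---|
| 0 | 0 | 100% | 92.7% |
| 1% | 0.7 | 99% | 92.2% |
| 2% | 1.4 | 98% | 91.7% |
| 5% | 3.5 | 95% | 90.1% |
| 10% | 7 | 90% | 86.7% |
| 20% | 14 | 80% | 78.0% |

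Both are calculations on means. The planned test for B cells, BLyS and autoantibodies is a rank ANCOVA, so they indicate scale only. Fewer than 70 and 140 will qualify, so each user weighs more than the table shows.

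**The case against.** The strongest objection is that cutting at rescue rituximab removes people because their disease worsened, which is informative. That is true, but the existing cut at re-start belimumab has the same property. It is an argument for reporting how many are cut, not for treating two rescues differently.

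It can also be said that affected participants are identifiable. Addendum 2 keeps Year 2 listings of concomitant medications and of medications leading to treatment failure (listings 21.05 and 21.06), and listings of biomarker results. A reader could find them, but the planned means, p-values and figures would still include their values.

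Three stronger readings are tempting and are not supported.

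- *Commercial belimumab also escapes the cut.* RAP Section 6.5 says of the exposure listings: "However they do not include concomitant medication of non-study belimumab or rituximab". Addendum 1, Section 2.8, says "Subjects can take commercial Belimumab IV or SC", but only for an LLDAS criterion. Against this, RAP Section 7.2.1 defines re-start as belimumab prescribed by the principal investigator, without naming a source of supply. RAP Section 15.6.15.9 adjudicates all Year 2 belimumab in Arms A and B as either a late dose or re-start. Commercial belimumab may therefore be cut. The text is ambiguous.
- *PK data would be read as a rituximab effect.* The end-of-study PK outputs are belimumab concentrations only. RAP Section 11.1 pools the three arms and plans no tests.
- *The B versus A difference must shrink.* Re-treatment in Arm B works the other way.

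**Conclusion.** The point holds for biomarkers after non-study rituximab. Followed as written, Section 2.3.2 leaves those values under the assigned arm, which conflicts with its own treatment of re-start belimumab and with the single-cycle objective. That the outputs would be taken as the effect of one cycle is inferred from the objective and the planned p-values; the documents do not say so.

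The size is unknown. Under the assumptions above, 90% to 99% of the difference survives when 1% to 10% of Arm A crosses over, so the effect is likely small unless use is common. These endpoints are exploratory and lie outside the testing hierarchy. The change is worth making because the rule is internally inconsistent and cheap to correct.

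**What to change.** In Addendum 2, Section 2.3.2, end each participant's biomarker data, in every arm, at the earlier of the existing cut and the first rituximab other than the study infusions. Report the number of participants cut, by arm. Re-run tables 25.01-25.09 and figures 25.01-25.04.

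In the same section, state that any non-study belimumab taken in Year 2 by Arms A and B counts as re-start for this cut, so that RAP Sections 6.5, 7.2.1 and 15.6.15.9 agree. PK table 26.01 would need re-running only if that statement changes which samples are kept.

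The cost is a sentence or two and the re-runs. Rituximab and belimumab are already identified in the medication coding (RAP Section 15.6.15.2). Some late observations are lost, and the loss is related to disease worsening, as with the present re-start cut.
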